5.6 Follow-Up After Subject Discontinuation of Study Drug or from Study

Discontinuation of Study Drug and Continuation of Study Participation

To minimize missing data for efficacy and safety assessments, subjects who prematurely discontinue study drug treatment should be encouraged to continue to be followed for all regularly scheduled visits as outlined in the [Appendix E](#), and adhere to all study procedures except for administration of study drug, annual TB testing, and PK sample collection, unless a subject decides to discontinue study participation entirely (withdrawal of informed consent). Subjects should continue to be advised on the scientific importance of their data even if they discontinue treatment with study drug early. Following the discontinuation of study drug, the subject should be treated in accordance with the investigator's best clinical judgment irrespective of whether the subject decides to continue participation in the study.

In addition, a 30-Day Follow-up Phone Call and a 70-Day Follow-up Visit after the last dose of study drug is required to ensure all treatment-emergent AEs/SAE have been resolved. All attempts must be made to determine the date of the last study drug dose and the primary reason for discontinuation of study drug or study participation. This information will be recorded on the appropriate eCRF page. This Follow-up Phone Call is not applicable for subjects who discontinue study drug prematurely and continue study participation with completion of at least 1 study visit at least 30 days after the last dose

of study drug. This Follow-up Visit is not applicable for subjects who discontinue study drug prematurely and continue study participation with completion of at least 1 study visit at least 70 days after the last dose of study drug.

Premature Discontinuation of Study (Withdrawal of Informed Consent)

If a subject prematurely discontinues study participation (withdrawal of informed consent), the procedures outlined for the Premature Discontinuation visit should be completed as soon as possible, preferably within 2 weeks, and preferably prior to initiation of another therapy.

For subjects to be considered lost to follow-up, reasonable attempts must be made to obtain information on the subject's final status. At a minimum, 2 telephone calls must be made, and 1 certified letter must be sent and documented in the subject's source documentation.

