Activity	Screening Day -35 to Day -1	Baseline Day 1	D Day 4	Wk 2 Day 15	Wk 4 Day 29	Wk 6 Day 43	Wk 8 Day 57	Wk 10 Day 71	Wk 12 Day 85	Wk 14 Day 99	Wk 16 Day 113	Wk 18 Day 127	Wk 20 Day 141	Wk 22 Day 155	Wk 24 Day 169	Double-Blind LTE Period 1			LTE Period 2			PD Visit	30-D F/U Phone Call	70-D F/U Visit
																EOW Visits	EGW Visits	Wk 78	Wk 86	ESW Visits	Wk 182			
																EOW Visits	EGW Visits	Day 547	Day 603	ESW Visits	Day 1,275			
12-lead ECG	✓								✓						✓		Wk 36	✓		Wk 134	✓	✓		
Chest x-ray	✓																Wk 54 if applicable			Wk 110 and 166 if applicable				
DXA (Bone Density, Body Composition) Scan	✓													✓				✓		Wk 134	✓			
Physician's Global Assessment of Disease Activity		✓	✓	✓	✓		✓		✓	✓		✓		✓	✓		✓	✓	✓	✓	✓	✓		
TJC68 and SJC66	✓	✓	✓	✓	✓		✓		✓	✓		✓		✓	✓		✓	✓	✓	✓	✓	✓		
Erythrocyte sedimentation rate	✓																							

Activity	Screening	Baseline	D 4	Wk 2	Wk 4	Wk 6	Wk 8	Wk 10	Wk 12	Wk 14	Wk 16	Wk 18	Wk 20	Wk 22	Wk 24	Double-Blind LTE Period 1			LTE Period 2			PD Visit	30-D F/U Phone Call	70-D F/U Visit
	Day -35 to Day -1	Day 1	Day 4	Day 15	Day 29	Day 43	Day 57	Day 71	Day 85	Day 99	Day 113	Day 127	Day 141	Day 155	Day 169	EOW Visits	EGW Visits	Wk 78	Wk 86	ESW Visits	Wk 182			
Urine pregnancy test (for female of childbearing potential)		✓			✓		✓		✓		✓		✓		✓	Wk 28, 32, 40, 44, 52, 56, 64, 68, 76	Wk 36, 48, 60, 72	Wk 78, 82	✓	Wk 90, 94, 98, 102, 106, 110, 114, 118, 122, 126, 130, 134, 138, 142, 146, 150, 154, 158, 162, 166, 170, 174, 178		✓		✓
																								
Serum pregnancy test (females of child-bearing potential): FSH, if applicable	✓																							
hsCRP	✓	✓	✓	✓	✓		✓		✓	✓		✓		✓	✓		✓	✓	✓	✓	✓	✓	✓	
TSH	✓																							
Anti-citrullinated protein antibody	✓																							

Activity	Screening	Double-Blind LTE Period 1														LTE Period 2						30-D F/U Phone Call	70-D F/U Visit		
	Day -35 to Day -1	Baseline	D 4	Wk 2	Wk 4	Wk 6	Wk 8	Wk 10	Wk 12	Wk 14	Wk 16	Wk 18	Wk 20	Wk 22	Wk 24	EOW Visits	EGW Visits	Wk 78	Wk 86	ESW Visits	Wk 182			PD Visit	
	Day 1	Day 4	Day 15	Day 29	Day 43	Day 57	Day 71	Day 85	Day 99	Day 113	Day 127	Day 141	Day 155	Day 169	EOW Visits	EGW Visits	Day 547	Day 603	ESW Visits	Day 1,275					
Rheumatoid Factor	✓														✓			✓			✓				
Hematology	✓	✓		✓	✓		✓		✓	✓		✓			✓		✓	✓	✓	✓	✓	✓		✓	
HbA1c	✓	✓							✓						✓		Wk 36, 48, 60, 72			Wk 94, 118, 142, 166	✓			✓	
Clinical chemistry and urinalysis	✓	✓		✓	✓		✓		✓	✓		✓			✓		✓	✓	✓	✓	✓	✓		Clinical chemistry only	

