Lipid profile		✓							✓						✓		Wk 36, 48, 60, 72			Wk 94, 118, 142, 166	✓				
TB Test (QuantiFERON TB Gold test and/or local lab purified protein derivative skin test)	✓																Only Wk 54			Wk 110 and 166					
HIV, HBV, and HCV Note: HBV test every 12 weeks only if required due to local regulations.	✓							✓							✓		E12W if applicable								

Activity	Screening															Double-Blind LTE Period 1			LTE Period 2			PD Visit	30-D F/U Phone Call	70-D F/U Visit	
	Day -35 to Day -1	Baseline	D 4	Wk 2	Wk 4	Wk 6	Wk 8	Wk 10	Wk 12	Wk 14	Wk 16	Wk 18	Wk 20	Wk 22	Wk 24	EOW Visits	EGW Visits	Wk 78	Wk 86	ESW Visits	Wk 182				
	Day 1	Day 4	Day 15	Day 29	Day 43	Day 57	Day 71	Day 85	Day 99	Day 113	Day 127	Day 141	Day 155	Day 169	EOW Visits	EGW Visits	Day 547	Day 603	ESW Visits	Day 1,275					
Blood samples for conjugated ADC (serum), total antibody (serum), free A-1677770 (plasma) assays		✓	✓	✓	✓		✓		✓			✓			✓		✓	✓	✓	✓	✓	✓			✓
Blood samples for serum ADA assays (including ADA titer and nAb, assays)		✓			✓		✓		✓			✓			✓		✓	✓	✓	✓	✓	✓			✓
Blood sample for total cortisol		✓	✓	✓	✓		✓		✓			✓			✓		✓	✓	✓	✓	✓	✓			✓
Biomarker sample whole blood for bone marker P1NP, OC, CTX, and BSAP		✓	✓	✓	✓		✓		✓			✓			✓		✓	✓							
Biomarker sample whole blood for free cortisol		✓	✓	✓	✓		✓		✓			✓			✓		✓	✓	✓	✓	✓	✓			✓
Biomarker sample whole blood for ACTH		✓			✓		✓		✓			✓			✓		✓	✓							
Biomarker sample whole blood for TBNK		✓	✓	✓			✓		✓			✓			✓		✓	✓							

Activity	Screening	Baseline	D 4	Wk 2	Wk 4	Wk 6	Wk 8	Wk 10	Wk 12	Wk 14	Wk 16	Wk 18	Wk 20	Wk 22	Wk 24	Double-Blind LTE Period 1			LTE Period 2			PD Visit	30-D F/U Phone Call	70-D F/U Visit
	Day -35 to Day -1	Day 1	Day 4	Day 15	Day 29	Day 43	Day 57	Day 71	Day 85	Day 99	Day 113	Day 127	Day 141	Day 155	Day 169	EOW Visits	EGW Visits	Wk 78	Wk 86	ESW Visits	Wk 182			
	Day -35 to Day -1	Day 1	Day 4	Day 15	Day 29	Day 43	Day 57	Day 71	Day 85	Day 99	Day 113	Day 127	Day 141	Day 155	Day 169	EOW Visits	EGW Visits	Day 547	Day 603	ESW Visits	Day 1,275			
Optional biomarker samples: plasma/serum proteomic		✓	✓	✓			✓		✓			✓			✓									
Optional biomarker samples: PBMC		✓	✓	✓			✓		✓			✓			✓									
Optional biomarker: samples: whole blood RNA		✓	✓	✓			✓		✓			✓			✓									
Optional biomarker: samples: whole blood DNA		✓	✓	✓			✓		✓			✓			✓									
Rx TREATMENT																								
Randomization/ drug assignment		✓							✓															
Supervised training for study drug administration at home																Wk 76		✓						

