Rationale: *To inform that subjects who opted for home dosing during the LTE Period 2 will have their diaries reviewed at specified visits to capture dosing dates and times for dosing compliance.*

- Operations Manual, Section 2.1 Individual Treatment Period Visits Activities Weeks 30, 36, 42, 48, 54, 60, 66, 72, 78, 86, 94, 102, 110, 118, 126, 134, 142, 150, 158, 166, 174: Added footnote "i" to inform the visit schedule for whole blood collection for free cortisol and bone markers.

Rationale: *To align with Activity Schedule (Appendix E).*

- Operations Manual, Section 2.1 Individual Treatment Period Visits Activities Week 182 Final Study Visit: Removed of PGIC – FLARE and bone biomarkers; added HbA1c and lipid profile; added note "a" to inform that subjects who opted for dosing at home will have their diaries reviewed. Changed notes and b to b and c, respectively.

Rationale: *PGIC – FLARE assessment at Week 178 will not be informative since it is based on the patient's recollection of disease activity at baseline and will continue to be collected at the Week 78 visit as previously planned. HbA1c and lipid profile were added to have a robust safety assessment at the updated final study visit at Week 182. To inform that subjects who opted for home dosing during the LTE Period 2 will have their diaries reviewed to capture dosing dates and times for dosing compliance. Footnotes b and updated to align with appropriate activities.*

- Operations Manual, Section 2.1 Individual Treatment Period Visits Activities Week 182 Final Study Visit: Added whole blood biomarker sample for free cortisol.

Rationale: *Whole blood biomarker sample for free cortisol was added to have a robust safety assessment at the updated final study visit at Week 182.*

- Operations Manual, Section 2.2 Post-Treatment Activities: 30-Day Post-treatment Follow-up Phone Call was added, which includes an AE assessment and prior and concomitant medications assessment.

Rationale: *Phone call was added to further ensure subject safety and capture of AEs/SAEs occurring early in the follow up period.*

- Operations Manual, Section 2.2 Post-Treatment Activities Post-Treatment Day 70 Visit: Added body weight, vital signs, whole blood biomarker sample for total and free cortisol, blood samples for serum conjugate ADC (serum), total antibody (serum), free A-1677770 (plasma) assays, and blood samples for serum ADA assays (including nAb), and ADA titer assays to the 70-day follow-up visit.

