Appendix B. Potentially Clinically Important Criteria for Safety Endpoints

The PCI criteria for selected laboratory variables are described in Table B1 instead of using NCI CTC.

Table B1. Potentially Clinically Important Criteria for Selected Laboratory Values

Laboratory Test	Category
HbA1c	< 6.5%
	≥ 6.5% to < 8%
	≥ 8%
HDL	< 1.03 mmol/L
	≥ 1.03 mmol/L
LDL	< 3.36 mmol/L
	≥ 3.36 to < 4.14 mmol/L
	≥ 4.14 mmol/L

The PCI criteria for selected vital sign variables (pulse rate, body temperature, and respiratory rate) are described in Table B2.

Table B2. Criteria for Potentially Clinically Important Vital Sign Values

Vital Sign	Category	Criteria for Potential Clinically Important Vital Signs
Pulse	Low	Value ≤ 50 bpm and decrease ≥ 15 bpm from Baseline
	High	Value ≥ 120 bpm and increase ≥ 15 bpm from Baseline
Body temperature	High	> 39.0 degrees C (102.3 degrees F)
Respiratory rate	Low	< 10 breaths/min
	High	> 24 breaths/min

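### Appendix E schedules no lipid profile, and apparently no HbA1c, at the Premature Discontinuation visit, so subjects who withdraw from the study before Week 12 have no scheduled post-baseline HDL or LDL and no on-drug HbA1c

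*Protocol*

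**What the plan says.** The gap has to be read from the current Activity Schedule in Protocol Appendix E. The row "Lipid profile" is ticked at Baseline, Week 12, Week 24, Weeks 36, 48, 60 and 72, Weeks 94, 118, 142 and 166, and Week 182. The HbA1c row has the same visits plus Screening, and one further tick in the last follow-up column. Hematology and clinical chemistry are ticked at PD as well as at follow-up; the chemistry and urinalysis row carries the note "Clinical chemistry only" in the last column.

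Appendix F gives the sponsor's reason for the Week 182 samples: "HbA1c and lipid profile were added to have a robust safety assessment at the updated final study visit at Week 182". This is amendment rationale. It shows the purpose of a last-visit sample, and it conflicts with nothing in the current text.

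Protocol 5.6 separates two groups. Subjects who stop study drug but remain in the study "should be encouraged to continue to be followed for all regularly scheduled visits as outlined in the" Activity Schedule. For subjects who withdraw from the study, "the procedures outlined for the Premature Discontinuation visit should be completed as soon as possible, preferably within 2 weeks". The text under the first group also says that "a 30-Day Follow-up Phone Call and a 70-Day Follow-up Visit after the last dose of study drug is required".

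SAP Appendix B states: "The PCI criteria for selected laboratory variables are described in Table B1 instead of using NCI CTC". Table B1 lists three tests: HbA1c, HDL and LDL.

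**The concern.** ABBV-154 carries a glucocorticoid receptor agonist, and the rationale in Protocol 2.1 is strong anti-inflammatory effect with fewer systemic glucocorticoid side effects. Protocol 2.2 names diabetes among the known adverse events of glucocorticoids, and criterion 4 in Protocol 5.1 admits subjects with HbA1c up to 8.5%. PCI laboratory values are a safety endpoint in SAP 3.4, and HbA1c, HDL and LDL are the only laboratory tests given their own PCI categories.

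Placebo subjects move to active drug at Week 12, so Week 12 is the only placebo-controlled post-baseline time point for these tests. A subject who leaves the study before then supplies nothing on lipids and nothing on-drug for HbA1c, although blood is drawn at the PD visit for other tests. A sample not taken at that visit cannot be recovered later.

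**Working it through.** No sample-size, power or alpha figure bears on this. The check is a column-by-column reading of Appendix E, followed by a count of scheduled samples.

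**Step 1: columns after Week 182.** The order in the schedule is PD Visit, 30-Day Follow-up Phone Call, 70-Day Follow-up Visit.

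| Row | Week 182 | PD | 30-day call | 70-day visit |
|---|---|---|---|---|
| Hematology | tick | tick | blank | tick |
| Clinical chemistry and urinalysis | tick | tick | blank | chemistry only |
| HbA1c | tick | blank | blank | tick |
| Lipid profile | tick | blank | blank | blank |

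**Step 2: how firm the reading is.** The lipid row has no entry after Week 182, so the lipid gap does not depend on how the last three columns are aligned. The HbA1c row does depend on it. In the extracted text the header of that table segment is disordered, and the PD label falls over the column that holds the last HbA1c tick. That same column holds the chemistry-only note, which comes after chemistry's own PD tick. This alignment points to the 70-day visit. Some other rows of the extracted table do drift: the DXA tick falls at Week 22, whereas SAP 10.6 gives Week 24, and the hepatitis B tick in this segment falls at Week 10. The HbA1c blank should therefore be checked against the original table.

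**Step 3: scheduled samples for a subject who withdraws from the study between Weeks 8 and 12 and attends the PD visit.**

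- Clinical chemistry: Weeks 2, 4, 8 and PD, so 4 post-baseline samples.
- HDL and LDL: 0 post-baseline samples.
- HbA1c: 0 on-drug samples, plus 1 at 70 days after the last dose if that visit takes place. SAP 10.2.1 equates 70 days with 5 half-lives, so this sample is off drug.

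**Step 4: what reaches the tables.** For such a subject the PCI counts and shift tables in SAP 10.3 have no HDL or LDL value. They have at most one off-drug HbA1c value.

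**Step 5: how many subjects.** The documents give no withdrawal rate. Taking 3% to 15% before Week 12 as an assumption:

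- Whole trial: 425 × 0.03 = 12.75 and 425 × 0.15 = 63.75, so about 13 to 64 subjects.
- Per arm: 85 × 0.03 = 2.55 and 85 × 0.15 = 12.75, so about 3 to 13 subjects.

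This counts study withdrawals only. Those who do not attend the PD visit would not be helped by any change to it.

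**Step 6: after Week 12.** The same blank means that the last value before withdrawal can be old. In the extension the intervals reach 94 − 72 = 22 weeks and 118 − 94 = 24 weeks. These gaps lie outside the placebo-controlled comparison.

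**The case against.** The strongest objection is that the protocol already keeps sampling the subjects of most interest. Someone who stops study drug because of a metabolic adverse event is encouraged to attend all scheduled visits, and Week 12 HbA1c and lipids remain due. The PD visit covers only withdrawal from the study. This stands, and it limits the point to that smaller group.

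Metabolic safety also has other cover. Chemistry is drawn at Weeks 2, 4, 8, 12 and PD, Protocol 2.2 commits to monitoring blood glucose, and glucocorticoid adverse events are adjudicated (Protocol 5.10). Neither HbA1c nor the lipid profile is an endpoint by name or carries a hypothesis test. All of this is fair. It lowers the priority but does not supply HDL, LDL or HbA1c for the subjects concerned.

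HbA1c after only a few weeks of exposure shows a partial drug effect, so a PD value is not equivalent to a Week 12 value. This is also true, but it does not touch the lipid part of the point.

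The SAP needs little change. Section 10.3 uses central and local laboratory data in all analyses and includes a shift to the final post-baseline value, with nothing that excludes PD samples. For the same reason the 70-day HbA1c could enter those tables.

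A reader might go further and infer that the Week 12 dose comparison is biased toward no difference, and put a number of percentage points on it. The documents do not support that. They give neither a withdrawal rate nor a difference in HbA1c or lipids between leavers and stayers, so any figure would be one assumption multiplied by another. It would also describe understatement within an arm. Bias in the difference from placebo would need withdrawal, or the excess among leavers, to differ between arms, and nothing in the documents speaks to that.

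**Conclusion.** The point holds as a sampling gap that is cheap to close, not as an error or an inconsistency in the plan. For subjects who withdraw from the study before Week 12, no post-baseline HDL or LDL is scheduled. On the most plausible reading of Appendix E, no on-drug HbA1c is scheduled either. The size, 3 to 13 subjects per arm, rests wholly on the assumed 3% to 15% withdrawal.

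Three things remain to be confirmed: the HbA1c cell at PD in the original table, whether the PD visit table in the Operations Manual agrees, and whether the chemistry panel already contains HDL or LDL. The last two cannot be seen in the documents. If the last HbA1c tick proves to be at PD, the HbA1c part falls away and the lipid part remains.

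**What to change.** In the PD Visit column of Appendix E, tick lipid profile, and tick HbA1c if the original table confirms that the cell is blank. Use the blood draw already taken for hematology and chemistry, and match the PD visit table in the Operations Manual. In SAP 10.3, a single sentence confirming that PD values enter the HbA1c, HDL and LDL summaries is enough.

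The cost is a schedule amendment and two extra assays on an existing draw, for withdrawals only. The limits are that HbA1c after short exposure will show only part of any effect, and that subjects who do not attend the PD visit still contribute nothing.

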1.0 Introduction

This Statistical Analysis Plan (SAP) describes the statistical analyses for ABBV-154 Study M20-466: A Randomized, Double-Blind, Placebo-Controlled Study to Evaluate the Safety and Efficacy of ABBV-154 in Subjects with Moderately to Severely Active Rheumatoid Arthritis with Inadequate Response to Biologic and/or Targeted Synthetic Disease-Modifying Anti-Rheumatic Drugs (b/tsDMARDs).

Study M20-466 assesses the efficacy and safety of ABBV-154 in subjects with moderately to severely active rheumatoid arthritis with inadequate response to biologic and/or targeted synthetic disease-modifying anti-rheumatic drugs (b/tsDMARDs).

The analyses of pharmacokinetic endpoints and pharmacodynamic biomarker endpoints will not be covered in this SAP.

The SAP will not be updated in case of administrative changes or amendments to the protocol that do not impact the analysis.

Unless noted otherwise, all analyses will be performed using SAS Version 9.4 (SAS Institute Inc., Cary, NC 27513) or later under the UNIX operating system.

2.0 Study Design and Objectives

2.1 Objectives, Hypotheses and Estimands

The primary objective is to assess the safety, tolerability, and efficacy of ABBV-154 vs. placebo on background methotrexate (MTX) for the treatment of subjects with moderately to severely active rheumatoid arthritis (RA) who have had an inadequate response to at least one prior b/tsDMARD.

The primary efficacy objective of the study is to demonstrate a higher rate of achieving 50% improvement as measured by American College of Rheumatology response criteria (ACR50) after 12 weeks of treatment with ABBV-154 when compared to placebo in the Intent-to-Treat (ITT) Population (further described in Section 4.0), which consists of all

randomized subjects who received at least one dose of study drug. The hypothesis corresponding to the primary efficacy objective and endpoint is that the proportion of subjects achieving ACR50 with ABBV-154 is greater than that with placebo at Week 12. The estimand for the primary endpoint is defined as the difference in the proportion of subjects achieving ACR50 at Week 12 in each of the ABBV-154 dose groups compared with the placebo group in the ITT Population.

The secondary efficacy objectives of the study are to demonstrate higher efficacy of treatment with ABBV-154 compared to placebo with respect to the secondary endpoints specified in Section 3.2 in the ITT Population. The estimands corresponding to the secondary efficacy objectives are as follow.

- For each of the categorical secondary endpoints, the estimands corresponding to the secondary efficacy objectives are defined as follows: Difference in the proportion of subjects achieving the endpoint in each of the ABBV-154 groups in comparison with the placebo group in the ITT Population.
- For each of the continuous secondary endpoints, the estimands corresponding to the secondary efficacy objectives are defined as follows: Difference in the mean change from baseline of the endpoint in each of the ABBV-154 dose groups in comparison with the placebo group in the ITT Population.

[figure not shown]
2.2 Study Design Overview

This is a randomized, double-blind, Phase 2b, dose-ranging study with a 12-week Placebo-Controlled Period, a 66-week Long-Term Extension (LTE) Period 1, and a 104-week LTE Period 2 in adults with moderately to severely active RA and on background MTX, who have had an inadequate response to b/tsDMARD treatment.

The Primary Analysis will be conducted after all ongoing subjects have completed Week 12 or withdrawn from the study. After the Primary Analysis, additional analyses may be conducted as needed. A final analysis will be conducted after all subjects have completed the LTE Period 2 and a safety follow-up visit 70 days after the last dose of

study drug, or have withdrawn from the study. The schematic of the study is shown in Figure 1.

Figure 1. Study Schematic

BL = Baseline; EOW = every other week; E4W = every 4 weeks; n = number of subjects; SC = subcutaneous

2.3 Treatment Assignment and Blinding

Subjects will remain on a stable dose of MTX until Week 24 (unless qualifying for rescue therapy as described in Protocol Section 5.4); thereafter MTX may be adjusted within the range of 7.5 – 25 mg/week. At Baseline, approximately 425 subjects will be randomized to 5 treatment groups in a 1:1:1:1:1 ratio to receive ABBV-154: 40 mg, 150 mg, 340 mg SC EOW; 340 mg SC E4W, or placebo. Randomization will be stratified by Baseline glucocorticoid (yes/no); number of prior failed b/tsDMARDs (1; 2 or more); and prior anti-TNF failure (yes/no) and if yes further stratification by prior adalimumab use (yes/no). At Week 12, subjects assigned to placebo will be re-randomized in a 1:1 ratio to receive ABBV-154 150 mg or 340 mg SC EOW; subjects from the other dose groups will continue with their respective dose and dosing regimen. Re-randomization will be stratified by Baseline glucocorticoid use (yes/no) and prior adalimumab use (yes/no). The

enrollment for subjects with prior adalimumab use is capped at approximately 30% of the total subjects enrolled. Systemic glucocorticoids (dose of ≤ 7.5 mg/d prednisone equivalent at Baseline) must be tapered off within 4 weeks of the start of study drug.

All AbbVie personnel with direct oversight of the conduct and management of the trial (except for AbbVie Drug Supply Management Team) will be blinded to each subject's treatment through Week 12. The AbbVie study team will be unblinded to treatment assignment for the Primary Analysis. This unblinding will take place after all subjects have completed the Week 12 visit or have withdrawn from the study prior to Week 12. To maintain integrity of the trial, the study site personnel and the subjects will remain blinded until all subjects have either completed the last visit of LTE Period 1 or have withdrawn from the study. Blinded dosing regimens will be continued until the previous criteria are met. To maintain the blind, the ABBV-154 and placebo pre-filled syringes provided for the study will be identical in appearance. The IRT will provide access to unblinded subject treatment information in the case of a medical emergency.

